## 4. Methods

### 4.1. RANDOMIZATION

No specific methods for assigning subjects will be used for this clinical investigation. A consecutive series of subjects at each site meeting all the eligibility criteria will be enrolled in this clinical investigation.

### 4.2. STATISTICAL INTERIM ANALYSES AND STOPPING GUIDANCE

Interim analyses will be performed on a yearly basis. The progress of the clinical investigation will be reported together with the interim results on the variable level according to the analysis plan.

The analysis of the primary endpoint / objective will be part of the related interim / annual report when all subjects have completed the 24 months postoperative including the ASES Shoulder Score.

There will be no stopping rules specified for this clinical investigation.

#### 4.3. TIMING OF FINAL ANALYSES

The full final report with complete analyses, progress and conduct reporting will be created at the end of this clinical investigation.

#### 4.4. TIMING OF OUTCOME ASSESSMENT

Subjects in this clinical investigation will be evaluated at Pre-Operative, Operative/Discharge, and at 6 Weeks (4 weeks – 8 weeks), 6 Months (23 weeks – 29 weeks), 12 Months (48 weeks - 56 weeks), 24 Months (100 weeks – 108 weeks) and annually thereafter. The follow-up evaluations will include assessment of device-related AEs/incidents, radiographs and ASES Shoulder Score.

Assessment	Preoperative	Operative/ Discharge	6 Weeks a, b (+/- 2 weeks)	6 Months a, b (+/- 3 weeks)	12 Months a, b (+/- 4 weeks)	24 Months a, b (+/- 4 weeks)	Annually b
Informed Consent	X						
Demographics & Medical History	X						
Inclusion/Exclusion	X						
Physical Exam	X		X c	X c	X c	X c	X c
Surgical Procedure		X					
ASES Shoulder Score	X		X d	X d	X d	X d	X d
Image Evaluation e, f	X	X	X	X	X	X	X
Subject Disposition g			X	X	X	X	X
	Device-Related AEs/Incidents & Reoperations will be collected throughout the course of the clinical investigation.						
	
 
a. Follow-up visit schedule to reflect Institutions' Standard of Care practices
 
b. If the subject misses a visit and is outside of the visit window, then every effort should be made to collect data instead of noting visit as missed.
 
c. Evaluation may be collected when subject presents in-clinic for study visit.
 
d. Evaluation can be collected via phone.
 
e. Radiograph collection should follow Institution's Standard of Care practices and no additional x-rays should be made for study purposes.
 
f. CT scans may be collected if part of Institution's Standard of Care practices.
 
g. Subject Disposition assessment will occur at any time point for subject withdrawal prior to the completion of the clinical investigation.
 
						

Table 4.4: Schedule of Events

#### 4.5. STATISTICAL SOFTWARE

Statistical analysis will be performed using IBM SPSS, IBM SPSS Sample Power as well as established standard software packages (e.g. MS Excel).

#### 4.6. MISSING DATA

The intent is to collect as complete a dataset as possible. Nevertheless, in some situations missing data cannot be avoided. The reports and tables therefore will show the number and percentage of missing cases for each analyzed variable in relation to the enrolled cases for each postoperative assessment.

Any deviations from Statistical Analysis Plan will be listed in the annual or final reports.

#### 4.7. CONFIDENCE INTERVALS AND P-VALUES

The following acceptance / rejection criteria were used for this clinical investigation:

Parameter	Acceptance / rejection criteria
Confidence level (1- $\alpha$ )	0.95 (95%)
Significance level ( $\alpha$ )	0.05 (5%)
Power (1- $\beta$ )	0.80 (80%)
Beta-level ( $\beta$ )	0.20 (20%)
Confidence interval of mean	95%
p-value indicating significance	$\leq 0.05$

Table 4.7: Acceptance / Rejection Criteria

#### 4.8. UNITS

See analysis chapter for details related to units used for the different variables and calculations.

In case of collection of variables with non-SI units (e.g. pounds instead to kilograms), conversion of such data into SI units (and vice versa) will be ensured and both results will be reported for the full set of available subjects next to each other in the interim/annual and/or final reports.

#### 4.9. CALCULATIONS AND TRANSFORMATIONS

Distances between times and differences between score results will be calculated. For full details of variables used for calculations and the creation of new variables based on these calculations, see Analysis chapter.

#### 4.10. ASSUMPTIONS

In case of deviation from assumptions (e.g. normality), non-parametric methods will be used for analysis. No transformation of such data will be performed.

### 5. Population and Progress

#### 5.1. ANALYSIS POPULATION

It is expected during this clinical investigation only one population for ReUnion RSA System will exist and all subjects will be analyzed “Per Protocol” (PP). However, it cannot be fully avoided that in theory subjects might need to be excluded from the PP population. In this occasion, there will be two groups being fully analyzed to ensure transparency and avoid bias.

The groups are defined as follows:

- **Intent-to Treat Population**

The Intent-to-Treat (ITT) Population is defined to be all enrolled subjects. An enrolled subject is a subject that has signed informed consent, all screening procedures have been successfully completed,

is eligible and can receive treatment. The ITT population will not be analyzed for the annual reports and will only be included in the final report.

- **Per Protocol Population**

The PP Population is defined to be all subjects in the ITT Population with no major protocol violations. The protocol deviations that will exclude a subject are as follows:

- The subject does not receive the ReUnion RSA System
- The subject does not meet all eligibility criteria
- The subject has a protocol deviation that is considered likely to affect subject outcomes.

After the clinical investigation has been completed, a review of the data will be conducted to determine which subjects are to be excluded from the PP population.

The following tables will be created for interim/annual and final reports related to the clinical investigation populations and progress:

Evaluation Variable / Question	Level of Measurement	Analysis Plan
All Forms – Overview & Progress Report		
Counting of available subjects Subject Population by Site (Variable(s): SITENUM; SUBID)	Qualitative, nominal	Proportions, frequencies, column and row totals, missing proportion (if any).
Counting of available subjects Subject Population by Visit (Variable(s): SITENUM; SUBID; VISITDT)	Qualitative, nominal	Proportions, frequencies, column and row totals, missing proportion (if any).
Counting of available subjects Subject Population by Visit and by Site (Variable(s): SITENUM; SUBID; VISITDT)	Qualitative, nominal	Proportions, frequencies, column and row totals, missing proportion (if any).

Table 5.1: Populations and Progress Tables List

## 5.2. ELIGIBILITY

A subject is defined as eligible if all inclusion and exclusion criteria are fulfilled as it is described in the clinical investigation plan. For details see CIP.

For tables to be created for the interim/annual and final reports, see chapter 6.2 and tables list 6.2.2.

## 5.3. WITHDRAWAL / FOLLOW-UP

During the clinical investigation if a subject must be withdrawn prematurely from the clinical investigation, then the procedures outlined in the CIP should be followed. These procedures should not interfere with the initiation of any new treatments that are necessary to treat a subject's condition. Information on all withdrawn subjects will be documented.

The following tables will be created for interim/annual and final reports related to the numbers of withdrawn subjects (if any):

Evaluation Variable / Question	Level of Measurement	Analysis Plan
All Forms – Overview & Progress Report		
Counting of withdrawn subjects Number of Subjects Withdrawn by Site (Variable(s): SITENUM; COMPPROT; PRIMRSN)	Qualitative, nominal	Proportions, frequencies, column and row totals, missing proportion (if any).
Counting of withdrawn subjects Number of Subjects Withdrawn by Site by Visit	Qualitative, nominal	Proportions, frequencies, column and row totals, missing proportion (if any).

(Variable(s): SITENUM; COMPPROT; PRIMRSN; VISITDT)		
Comments related to Reasons for Subjects Withdrawn (Variable(s): RSNSPF)	Text, String	Listing of reasons for subjects being excluded by subject code/ID

Table 5.3: Withdrawal Tables List

#### 5.4. ADHERENCE AND CIP DEVIATIONS

Any CIP deviations will be listed in the interim/annual and final reports. It is optional to describe this chapter in free text or present it in a tabulated format.

### 6. Analysis

The following tabulated analysis plan reflects this approach and specifies the variable's characteristics (quantitative or qualitative) in detail together with the related analysis strategy. This also includes calculations and summaries based on primary elements and the required analysis.

In addition, it will be defined in the text or directly in the tables below, if the variable must be included in an interim/annual report (IR) and/or in the final report (FR).

#### 6.1. HARMS AND SAFETY

Categorization and definitions of (Serious-, Unanticipated-) Adverse Device Effects, (Serious-) Incidents are given in the CIP.

Evaluation Variable / Question	Level of Measurement	Analysis Plan	Inclusion		
			IR	FR	N/A
Adverse Events / Incidents					
Perioperative/Postoperative AE (Variable(s): PERPOST)	Qualitative, nominal	Proportions, frequencies, column and row totals, missing proportion (if any).	X	X	
Device-Related Adverse Event / Incident (Variable(s): AEEVENT; AEOTHER)	Qualitative, nominal	Proportions, frequencies, column and row totals, missing proportion (if any). Listing of other Events/Incidents.	X	X	
Describe the AE/Incident (Variable(s): AEDESCRP)	Qualitative, nominal	Listing of other Events/Incidents Description.			X
Unanticipated Adverse Device Event? (Variable(s): AEUADE)	Qualitative, nominal	Proportions, frequencies, column and row totals, missing proportion (if any).	X	X	
Severity (Variable(s): AESEVER)	Qualitative, nominal	Proportions, frequencies, column and row totals, missing proportion (if any).	X	X	
Action Taken (Variable(s): ACTNONE; ACTMEDS; ACTSURG; ACTSHORT; ACTPROHS; ACTOTHER; ACTOTHSP)	Qualitative, nominal	Proportions, frequencies, column and row totals, missing proportion (if any). Listing of given Other specifications.			X
AE Resolution (Variable(s): AERESOLV)	Qualitative, nominal	Proportions, frequencies, column and row totals, missing proportion (if any).			X
Outcome (Variable(s): AEONWOTR; AEONWTTR; AEREWOTR; AEREWTTR; AEATEDISB; AEPERMD; AESUEXP)	Qualitative, nominal	Proportions, frequencies, column and row totals, missing proportion (if any).			X
Creation of variable Number of Adverse Device Effects by Site (Variable(s): AEEVENT; SITENUM)	Qualitative, nominal	Proportions, frequencies, column and row totals, missing proportion (if any).	X	X	

Creation of variable Number of Adverse Device Effects per Subject and Site (Variable(s): AEEVENT; SITENUM; SUBID)	Qualitative, nominal	Proportions, frequencies, column and row totals, missing proportion (if any).	X	X	
---	----------------------	---	---	---	--

Table 6.1.1: Adverse Events / Incidents Tables List

Evaluation Variable / Question	Level of Measurement	Analysis Plan	Inclusion		
			IR	FR	N/A
Reoperation					
Type of Procedure (Variable(s): IRRDEB; SOFTTRL; SOFTTRP; REVRSA; REVRSADT; REVRSADT_DEC; CONHEMW; CONHEMW0; REFINF; REVINF; REVINF_DEC; RESARTH; ARTHOD; ORIF; RESOSSIF; TYPEOTH; OTHSPC)	Qualitative, nominal	Proportions, frequencies, column and row totals, missing proportion (if any). Listings of implant specifications.	X	X	
Reason(s) for Reoperation (Variable(s): WOUNCOM; INFEC; NERPAL; DISLC; SUBLUX; IMPDISL; IMPLOOS; IMPBRKG; MALPOS; UNDROVR; PERFRAC; STIFF; PAIN; HETOSSIF; RESOTH; OTHRSPC)	Qualitative, nominal	Proportions, frequencies, column and row totals, missing proportion (if any). Listings of other specifications.	X	X	

Table 6.1.2: Reoperation Tables List

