8.2. SECONDARY ENDPOINT

In addition to the principal endpoint, information on the following outcomes will be assessed up to 10 years after the index procedure:

Safety: Incidence of device-related intra-operative and post-operative AEs

Efficacy/Performance: Implant survivorship will be monitored

9. Selection of Clinical Investigation Population

Subjects participating in this clinical investigation will be recruited from the investigator's standard subject population, where all patients presenting for primary or revision total shoulder replacement will be evaluated for clinical investigation participation based on the eligibility criteria listed below.

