13.3. RELATIONSHIP TO THE DEVICE

Only events considered possibly, probably or definitely related to the device will be captured for this clinical investigation.

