### 3.1.2. Secondary Analyses

The incidence of device-related AEs and implant survivorship will be assessed up to 10 years after the index procedure and monitored through collection and analyses.

Furthermore, time to (earliest) device-related AEs will be analyzed as well. For analysis of the time to the (earliest) device-related AEs as well as the time to secondary procedure (revision, removal, reoperation), the Kaplan-Meier method will be used. Considered variables, the level of measurement and the planned analysis steps are listed in detail in the SAP. These analyses will be part of the final report.

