### 7.1. FREQUENCIES

All answered response options must be listed with the appropriate label, other response options do not have to be displayed necessarily. In the event of missing answers, the frequencies must be included in an extra row as well (“Missing”). All given answers must be added up in an extra row (“Total”). In addition to the number of frequencies, percentages must be displayed in a separate column.

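### SAP Table 6.1.1 names no denominator and no interval for device-related AEs, so incidence by event type and by perioperative/postoperative category is not estimated

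*SAP*

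**What the plan says.** CIP 8.2 gives the endpoint as "Safety: Incidence of device-related intra-operative and post-operative AEs". SAP 3.1.2 adds the horizon: "The incidence of device-related AEs and implant survivorship will be assessed up to 10 years after the index procedure". CIP 13.3 limits what reaches the AE form: "Only events considered possibly, probably or definitely related to the device will be captured".

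In SAP 6.1, Table 6.1.1, the event-type row "Device-Related Adverse Event / Incident (Variable(s): AEEVENT; AEOTHER" is to be analysed by "Proportions, frequencies, column and row totals, missing proportion (if any). Listing of other Events/Incidents". The PERPOST row has the same plan without the listing. Both rows go into the interim and final reports. Neither names a denominator or an interval.

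The SAP 7.1 template has columns for n and % only. On the total row it says "All given answers must be added up in an extra row", and on options that nobody recorded it says "other response options do not have to be displayed necessarily". The one interval entry in SAP 4.7 is "Confidence interval of mean".

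Two planned analyses do work per subject. The last row of Table 6.1.1 counts adverse device effects by subject and site, for interim and final reports. Table 6.6.2 plans a Kaplan-Meier analysis of time to the first device-related AE of any type. It gives the standard error of the estimate, and a 95% interval for mean survival time only.

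On timing, CIP 11.3.3 puts the analyses of AE incidence and survivorship in the annual and final reports. SAP 3.1.2 puts the secondary analyses, including the Kaplan-Meier, in the final report.

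**The concern.** Incidence needs subjects at risk in the denominator. A percentage computed over AE records answers another question, namely how the recorded events divide among types. It moves with the number of other events, and it counts a subject with repeated events more than once. A reader of an annual report could take such a figure for the incidence of dislocation or infection. Without an interval, the reader also cannot see how little about 80 subjects can say on a rare failure mode, or what a count of zero excludes.

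**Working it through.** The documents give no AE rate, precision target or sample size for this endpoint, so there is no plan figure to reproduce. The event counts below are assumptions chosen for illustration.

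**Step 1: what denominator follows from the text.** Table 6.1.1 is silent. SAP 7.1 totals the given answers. An AE form is filled in only when a device-related event is captured (CIP 13.3), so the given answers for AEEVENT and PERPOST are recorded events. SAP 4.6 is the only missing-data text that refers to enrolled cases, and it does so for missing values at each postoperative assessment. Applied to an AE table, it would class event-free subjects as missing, which is not incidence either.

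**Step 2: what each planned analysis delivers.**
- AEEVENT and PERPOST rows: counts and percentages, no subject denominator, no interval.
- Effects by subject and site: shows which subjects had an event, so an overall count can be made. It is not by type and has no interval.
- Table 6.6.2: one minus the curve is overall subject-level cumulative incidence, with a standard error. It is not by type or by PERPOST category.
- Table 6.5.4: radiographic findings visit by visit. These are proportions at a visit for some event types, not cumulative incidence.

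**Step 3: effect of the denominator.** Inputs: 80 subjects (enrolment target, SAP 3.2, all assumed implanted and fully followed) and 5 dislocations in 4 subjects (assumed).
- Share of events, 20 recorded: 5/20 = 25%.
- Share of events, 40 recorded: 5/40 = 12.5%.
- Subject incidence in both cases: 4/80 = 5.0%. The exact (Clopper-Pearson) limits are the 0.025 quantile of Beta(4, 77) and the 0.975 quantile of Beta(5, 76), giving 1.4% to 12.3%.

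With 3 subjects having one event each, incidence is 3/80 = 3.75% (0.8% to 10.6%). The share of events is 3/6 = 50%, 3/12 = 25% or 3/24 = 12.5%, depending on the total recorded.

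**Step 4: zero events, and the effect of drop-out.** For 0 of n, the two-sided 95% upper limit is 1 − 0.025^(1/n).
- n = 80: 1 − 0.025^(1/80) = 4.5%.
- SAP 3.2 assumes 56% overall drop-out, and 80 × (1 − 0.56) = 35.2. With n = 35: 1 − 0.025^(1/35) = 10.0%.

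The bound of 4.5% therefore needs complete follow-up. The documents do not say by what time the 56% is reached, so 35 subjects is an assumption about late follow-up. A crude proportion over 80 counts lost subjects as event-free and so understates late incidence.

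**The case against.** The best defence is that the SAP never says its percentages are shares of events. SAP 7.1 is a generic template that also serves variables such as gender. This stands: the accurate statement is that the denominator is not specified and that the template, followed literally, leads to recorded events.

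A reader might go further and infer that the SAP estimates no incidence at all. The documents do not support that. The by-subject row lets affected subjects be counted, and the Kaplan-Meier analysis of the first event estimates the overall endpoint with a standard error. Reoperation has its own curve in SAP 6.7.3.

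It is also true that the endpoint wording does not ask for incidence by type. But Table 6.1.1 tabulates type and prints a percentage beside it, so the meaning of that percentage has to be fixed.

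A reader might also infer that zero-count event types are lost. SAP 7.1 requires every recorded option to be shown, so an absent type had no events, and several failure modes recur as radiographic items. What is lost is an explicit zero with its upper bound.

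Finally, PERPOST does tabulate a split by period. It lacks a subject denominator, and its perioperative category is not the same as the endpoint's intra-operative one: CIP 13.5 lists thrombosis, embolism and infection as perioperative.

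**Conclusion.** The concern holds in a limited form. Table 6.1.1 leaves the denominator open for AEEVENT and PERPOST, and the template would turn the percentages into event shares. No planned analysis gives subject incidence by event type or by PERPOST category, and none attaches a confidence interval to an incidence. Overall incidence is available, but through a Kaplan-Meier analysis that SAP 3.1.2 places in the final report, whereas CIP 11.3.3 promises incidence annually as well.

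The size depends on the counts. In the illustrations, a subject incidence of 5.0% prints as 25% or 12.5%, and one of 3.75% prints as anything from 12.5% to 50%. These rest on assumed events and on 80 fully followed subjects. The zero-event bound runs from 4.5% with complete follow-up to about 10% with about 35 subjects remaining. The primary endpoint is not affected. The change should be made, because it concerns a named endpoint and is cheap.

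**What to change.** In Table 6.1.1, for interim and final reports:
- For any event, each AEEVENT type and each PERPOST category, report subjects with at least one event over subjects implanted. Put event counts in a separate column.
- Print a row for every event listed in CIP 13.5, including zeros.
- For perioperative events, where follow-up should be essentially complete, give an exact 95% CI.
- For later events, give 1 minus Kaplan-Meier of time to first event of that type, with pointwise 95% CI and number at risk at fixed times (for example 24 months, 5 and 10 years, as reached). Do not use a crude proportion over 80 for long-term incidence.
- Use PERPOST as collected, and say that it carries the endpoint's period split. A split at the day of surgery would cut across the perioperative list in CIP 13.5.

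Reconcile CIP 11.3.3 (annual and final) with SAP 3.1.2 and Table 6.6.2 (final only).

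The cost is SAP wording and one subject-level derivation from SUBID, AEEVENT, PERPOST and AEONSTDT, all of which the SAP already names. No new data are collected. The downside is somewhat more analysis work and intervals that will be wide.

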The 24 months post-operative results for subjects implanted with the ReUnion RSA System will be compared to a historical group and results reported by respective clinical outcome data in the scientific literature. The benchmark sources and values will serve as the control group for the ReUnion RSA System subjects.

Hypotheses are developed to allow for a comparison of 24 months post-operative ASES score results and 24 months effectiveness/performance between these two populations.

The Statistical Analysis Plan (SAP) lists all variables/questions within this clinical investigation. Therefore, no additional “evaluation” chapter is required nor needed for this CIP.

Data will be captured via IBM Clinical Development electronic data capture (EDC) system and statistical analysis will be performed using IBM SPSS. All statistical hypotheses tests will be with confidence levels ($1-\alpha$) of 95% and power ($1-\beta$) of 80%. The significance level (α) is 0.05 and the beta-value (β) is set to 0.20. Therefore, p -values ≤ 0.05 will indicate statistical significance.

Results will be presented using summary tables and optionally supported by graphs. For detailed information per variable, see SAP.

The primary endpoint of the clinical investigation is to demonstrate non-inferiority of the device to the selected literature controls, as measured by the ASES Shoulder Score at 24 Months post-operative. Specifically, the proposed study will test the null hypothesis that the population mean is 71.27 points. The criterion for significance (alpha) is set at 0.05. With the sample size of 10 cases, the clinical investigation will have power of 80.3% to yield a statistically significant result. This computation assumes that the population from which the sample will be drawn has a mean of 71.27 points with a standard deviation of 19.40 points. The observed value will be tested against a theoretical value (lower limit - θ) of 51.87 points. To account for an estimated appropriate overall drop-out rate, Stryker intends to enroll the calculated number of subjects, multiplied by the number of cleared indications (four) to reflect the underlying subject population adequately.

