13.1. DEFINITIONS

- **An Adverse Device Effect (ADE)** is defined as any untoward or unintended response to the clinical investigation treatment; and/or a medical response which may have a causal relationship to the treatment.
- **An Incident** is defined as any malfunction or deterioration in the characteristics or performance of a device made available on the market, including use-error due to ergonomic features, as well as any inadequacy in the information supplied by the manufacturer and any undesirable side-effect.
- **A Serious Adverse Device Effect (SADE)** is defined as any ADE that results in consequences characteristic of a SAE or might lead to the consequences if suitable action or intervention is not taken; causes considerable interference with the subject's usual activities and may be incapacitating or life-threatening, including those events resulting in a subject's disability or permanent damage, or required intervention to prevent disability or permanent damage; results in a life-threatening illness or injury; and/or results in death (fatal).
- **A Serious Incident** is defined as any incident that directly or indirectly led, might have led or might lead to any of the following:
 - the death of a patient, user or other person;
 - the temporary or permanent serious deterioration of a patient's, user's or other person's state of health;
 - a serious public health threat
- **An Unanticipated Adverse Device Effect (UADE)** is defined as an AE not described in the informed consent, CIP or device labeling which has resulted in any of the consequences of a SAE or which might have led to any of the consequences of a SAE if suitable action had not been taken, intervention had not occurred, or if circumstances had been less opportune.

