13.4. ADVERSE EVENT/INCIDENT REPORTING

In the event a SADE, UADE or serious incident occurs, the Investigator is required to notify the Sponsor within 48 hours of being made aware of the event. The Investigator also is required to notify their IRB in accordance with the policies of their local laws and regulations.

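### SAP Table 6.1.1 leaves adverse event outcome, action taken and resolution out of every report and plans no count of serious device effects or serious incidents, so seriousness can only be approximated from severity

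*SAP*

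**What the plan says.** Section 6 of the SAP explains that the IR and FR columns of its tables show which variables must go into the interim/annual and final reports. It does not define the N/A column. In Table 6.1.1 four items carry a mark under N/A only: the event description, "Action Taken (Variable(s): ACTNONE; ACTMEDS; ACTSURG; ACTSHORT; ACTPROHS; ACTOTHER; ACTOTHSP"), "AE Resolution (Variable(s): AERESOLV") and "Outcome (Variable(s): AEONWOTR; AEONWTTR; AEREWOTR; AEREWTTR; AEATEDISB; AEPERMD; AESUEXP"). Perioperative/postoperative timing, event type, the flag for an unanticipated adverse device effect (UADE), severity, and the two derived counts (by site, and per subject and site) are marked for both reports.

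On seriousness, SAP 6.1 says only this: "Categorization and definitions of (Serious-, Unanticipated-) Adverse Device Effects, (Serious-) Incidents are given in the CIP". The protocol (the CIP) defines a SADE in section 13.1 as "any ADE that results in consequences characteristic of a SAE or might lead to the consequences", followed by further consequences, and defines a serious incident separately. Section 13.4 makes both notifiable: "In the event a SADE, UADE or serious incident occurs, the Investigator is required to notify the Sponsor within 48 hours". Section 11 of the protocol states: "The Statistical Analysis Plan (SAP) lists all variables/questions within this clinical investigation". No SAP table contains a row for a SADE or a serious incident.

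For frequency tables, SAP 7.1 says of the total row: "All given answers must be added up in an extra row". The secondary safety endpoint in protocol 8.2 is an incidence of device-related events.

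**The concern.** Safety is half of the stated objective, and the protocol synopsis says it will be shown through the reporting of device-related events. Protocol section 13 ties the study to European post-market requirements and to incident categories. A reader of such a safety report will want to know how many subjects had a serious device effect, how events ended, and what proportion of implanted subjects had each type of event. If the SAP is followed exactly, none of its tables is built to answer these questions directly. The data on how events ended are collected and then left out, and the categories that the protocol makes notifiable have no table. The event-type and severity percentages have a denominator that does not match an incidence.

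**Working it through.** The plan states no figure that needs reproducing. The check compares passages, with one short calculation.

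**1. Rows of Table 6.1.1**

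| Row | Interim and final | N/A only |
|---|---|---|
| Perioperative/postoperative | x | |
| Event type | x | |
| Description | | x |
| UADE flag | x | |
| Severity | x | |
| Action taken | | x |
| Resolution | | x |
| Outcome | | x |
| Derived: number by site | x | |
| Derived: number per subject and site | x | |

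N/A only: 4 of 10 rows, or 4 of 8 once the two derived rows are set aside. This is a count of rows in this table, not of items on the adverse event form: the onset date is also collected and is used in Table 6.6.2. From their names, the outcome codes appear to cover ongoing or resolved with or without treatment, disability, permanent damage and death, but the documents do not spell them out. The eligibility rows in Table 6.2.1 are also N/A, but there a note says they will be covered by a statement. The adverse event rows have no such note.

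**2. What the planned reports capture of seriousness**

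Protocol 13.1 set against the severity scale in 13.2, which is reported in both reports:

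- Considerable interference, incapacity, disability, permanent damage or intervention to prevent it: matched by the Severe grade.
- Life-threatening illness or injury: matched by the Life-Threatening grade.
- Death: matched by the Fatal grade.
- Consequences of the kind that make an event an SAE: no match, and 13.1 uses SAE without defining it.
- Events that might have had such consequences without action or intervention: no match.
- Serious incidents, a separate definition that includes potential harm and public health threats: no match.

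The grades also overlap. The definition of Severe already takes in events that may be life-threatening, while Life-Threatening is a grade of its own.

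The other planned items do not fill the gap. A UADE is by definition an event not described in the consent form, the protocol or the labeling. Deep infection, pulmonary embolism and periprosthetic fracture are all listed as foreseeable in protocol 13.5, so none of them can be a UADE however serious. The reoperation tables miss serious events managed without surgery. The mortality analysis counts all deaths and is not tied to device-related events.

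**3. Denominator**

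Under the generic template, the percentage for an event type is k/E, where k is the number of events of that type and E is all reported events. The incidence is s/N, where s is the number of subjects with at least one such event and N is the number implanted. Take N = 80 (the enrollment target) and assume k = s = 4. The documents give no expected event counts, so E is varied:

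- E = 8: 4/8 = 50%
- E = 16: 4/16 = 25%
- E = 40: 4/40 = 10%
- Incidence in every case: 4/80 = 5%

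The template percentage thus depends on how many other events were reported, while the incidence does not.

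**The case against.** The strongest reply is that much of the safety picture is planned. Severity is in both reports and its top three grades repeat most of the SADE wording. The UADE flag and the type and reason of reoperation are also in both, and mortality is in the final report. Table 6.6.2 specifies a Kaplan-Meier analysis of time to first device-related event, with one event or censoring per subject, and Table 6.1.1 gives counts per subject. Overall subject-level incidence is therefore available, and the endpoint text promises no breakdown by type or seriousness. All of this stands. A reader might infer that serious device effects cannot be reported at all, and the documents do not support that: severity is an incomplete proxy, not an absent one, and the N/A data are collected and recoverable.

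A reader might also infer that the lack of a relatedness variable is part of the cause. It is not. Protocol 13.3 admits only events possibly, probably or definitely related to the device, so every tabulated event is already device-related. Only the three-level grading is lost, and nothing in the plan promises to report it. Nor is the 48-hour duty at risk, since it runs from investigator to sponsor and depends on no SAP table.

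Finally, the eCRF is not among the documents. The SAP list is visibly incomplete (Table 6.3.2 has no row for the baseplate, although it is a system component), so a seriousness field may exist. That is a fair limit on the claim: what can be said is that the SAP lists no such variable. Section 7.1 is likewise a generic layout that does not discuss adverse event denominators. But no other denominator is specified for the by-type and by-severity tables.

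**Conclusion.** The point holds as a gap in planned reporting that should be corrected. It does not mean that the safety data are lost. Four of the 8 non-derived rows in Table 6.1.1 are in no planned report, so the reports omit how events ended. No SADE or serious-incident count is planned, although SAP 6.1 refers to these categories and the protocol makes them notifiable. Serious device effects can be approximated from severity, but two limbs of the SADE definition and all serious incidents fall outside it. Overall incidence is covered; subject-level percentages by type, severity and seriousness are not.

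This rests on three assumptions: that the IR and FR columns decide report content, as SAP section 6 says; that no seriousness derivation exists outside the documents; and that the outcome codes mean what their names suggest. The percentages in the denominator illustration use assumed event counts and are not a forecast.

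**What to change.** 1. In Table 6.1.1, mark action taken, resolution and outcome for at least the final report.
2. Add a tabulation of SADEs and serious incidents. Use the eCRF field if one exists. Otherwise add a field, or state a derivation that draws on the 48-hour notifications.
3. Define SAE in protocol 13.1, and reconcile the overlap between the Severe and Life-Threatening grades in 13.2.
4. Report device-related events by type, severity and seriousness as the number and percentage of implanted subjects with at least one event, next to the event counts.

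The first change is a different tick against data already collected. The others cost a few extra tables, some protocol wording, and possibly one or two fields back-filled from notifications and source records.
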